## 2.0 Background

---

### 2.1 Introduction/Rationale for Development

#### 2.1.1 Chronic GVHD

Allogeneic hematopoietic stem cell transplantation (allo-HCT) is a proven effective immunotherapy for aggressive hematologic cancers that is used increasingly worldwide. Clinical outcomes post allo-HCT, including relapse, non-relapse mortality and overall long term survivorship have been improving for the past two decades and this is attributed to better donor selection, supportive care, less toxic conditioning regimens and advancements in management of acute and chronic graft versus host disease (GVHD).

Despite these advances, allo-HCT continues to be associated with clinically significant morbidity and mortality, most of which is attributed to acute and chronic GVHD. Glucocorticoids are the first line of therapy and responses are seen in about one-third of patients with cGVHD. Patients with cGVHD that is refractory to steroids are particularly difficult to treat as there is currently no standard of care. Effective therapies for steroid-refractory cGVHD are an unmet medical need and new strategies should be aimed towards alleviating symptoms and improving long term survivorship.

The underlying pathophysiologic mechanisms of cGVHD are complex and are related to the transplanted donor T-cells recognizing the recipient as “non-self” based on a variety of factors, the most important of which is degree of HLA disparity between donor-recipient pair. ChronicGVHD is comprised of an early initiating phase, followed by gradual evolution to the full blown syndrome, which can involve multiple organs. The “prime targets” are skin, GI tract and liver, which undergo tissue damage as part of the preceding chemotherapy and conditioning regimens. Other organs such as lung, salivary and lacrimal glands, oral mucosa, skin and subcutaneous tissues can also be involved and contribute to morbidity associated with cGVHD. During the initiation phase of cGVHD, recipient antigen presenting cells (rAPC's) engage Donor CD8+ T cells by presenting self antigens in conjunction with the MHC class I complex. Donor CD4+ T cells are activated by the MHC class II pathway, wherein, shed donor proteins and apoptotic cells are processed by endosomes and presented to Donor CD4+ cells by rAPC's. After antigen presentation and appropriate co-stimulatory signaling, donor CD4+ and CD8+ T cells undergo activation and expansion. In the evolution phase, donor APC's continue the ongoing activation of donor-

derived T cells by presenting recipient antigens via MHC class I and II peptides. The activated T cells cause tissue damage by release of cytokines (TNF- $\alpha$ , IL-2, IFN- $\gamma$ ) and by direct tissue infiltration.

Steroid refractory cGVHD is treated by a number of second-line immunosuppressive drugs including calcineurin inhibitors, sirolimus, mycophenolate mofetil, alemtuzumab, rituxan, tyrosine kinase inhibitors, proteosome inhibitors, etanercept and infliximab. There is no current standard of care for second-line therapy, so development of new agents and novel combinations of existing therapies for second-line GVHD therapy is an urgent need.

Evaluation of patients with cGVHD using validated and standardized response criteria is lacking at the present time and this is a major drawback while evaluating response to therapy across clinical trials. Inamoto et al. recently described a new outcome measure, failure-free survival (FFS), to access response to second-line agents in patients with cGVHD. Failure events include non-relapse mortality, recurrent malignancy, and change in systemic therapy. FFS is a meaningful clinical metric that could be used as a shorter-term success end point for clinical trials. In their analysis of 312 patients with cGVHD who were on at least 0.5 mg/kg of prednisone equivalent and started on second-line immunosuppressive therapy, the 6 month FFS was 56%. The majority of failures were due to initiation of third line therapy (34%) indicating progression of cGVHD, 7 % were due to NRM and 3% due to disease relapse. Predictors of treatment failure were high-risk disease at HCT, lower GI involvement and high NIH global score at initiation of second-line therapy. FFS will be included as a secondary end point in our cohort.

### 2.1.2 Extracorporeal photopheresis (ECP)

Extracorporeal photopheresis (ECP) has emerged as a promising modality to treat steroid refractory cGVHD. The procedure entails ex vivo treatment of leukapheresed patient lymphocytes with a photoactivatable compound and irradiation by ultraviolet A (UVA), followed by reinfusion of treated white blood cells (WBCs) back into the patient. ECP was initially applied in the treatment of cutaneous T-cell lymphoma (CTCL) and subsequently also in the treatment of acute and chronic graft-versus-host disease (GVHD), autoimmune disorders, and heart and lung transplant rejection. The clinical efficacy of ECP has been attributed to an immune modulatory effect and selective immune tolerance in some cases. The exact mechanism remains unknown; however, the following mechanisms of action are proposed;

- Clearance of apoptotic cells by antigen-presenting cells results in differentiation of those cells into a more tolerogenic phenotype leading to decreased stimulation of effector T cells or their deletion.
- Production of anti-inflammatory cytokines, especially interleukin 10, is increased
- Production of pro-inflammatory cytokines, especially interleukin 12 and TNF $\alpha$ , is decreased.
- Generation of CD4+, CD25+, GITR+, Foxp3+, CD62L+ T-regulatory cells.
- Generation of monocyte-derived, tolerogenic dendritic cells has been postulated to contribute to the downregulation of immune response in GVHD.

One study evaluated the percentage of functional T-regs after 6 ECP procedures demonstrating an increase from 8.9 to 29% of the total circulating CD4+ cells. ECP is an apheresis-based therapy, where approximately  $5 \times 10^9$  transplant-recipient leukocytes are treated with a photoactivatable 8-methoxysoralen (8-MOP), followed by exposure to approximately 1.5 Joules/cm^2 of UVA light and reinfusion of treated leukocytes to recipients in a closed-loop system.

Flowers et al reported a multicenter Phase II randomized study of ECP for patients with cGVHD. 95 patients with refractory cutaneous cGVHD were enrolled to this trial that compared standard therapy to standard therapy plus ECP given for 12-24 weeks. The median percentage improvement in total skin score (TSS) at week 12 was 14.5% for the ECP arm and 8.5% for the control arm ( $P = .48$ ). No complete remissions were seen. The proportion of patients who had at least a 50% reduction in steroid dose and at least a 25% decrease from baseline in TSS was 8.3% in the ECP arm at week 12 and 0% in the control

arm ( $P = .04$ ). The authors concluded that ECP was a well-tolerated modality and was associated with a significant steroid sparing effect. The short duration of therapy (12 weeks) contributed to the lack of statistically significant reductions in TSS and authors recommended longer duration of therapy for up to 24 weeks. Infections were the most serious side effect occurring in 18.4% of patients on ECP arm versus 26% in patients assigned standard therapy. Pneumonia and sepsis were the most common infectious complications. 2% mortality was noted in this study in the ECP arm and 6% in standard therapy arm. Improvements were also noted in extracutaneous sites of involvement including eye (30% ORR) and oral cGVHD (53%).

Malik et al. reported a meta-analysis of 18 trials to access the efficacy of ECP in the steroid refractory cGVHD setting. Their analysis included one randomized controlled trial, two single arm prospective studies and the remainder were retrospective studies. The pooled complete response rates were 29% (CI, 19-42%) and overall response rates were 64% (CI, 65-82%). The responses varied according to organ involvement with response rates of 74%, 68%, 60%, 48%, 72% and 53% for skin, liver, ocular, lung, oral, and GI steroid refractory-cGVHD respectively. The main drawbacks in this study were the limited number of prospective trials and variability in duration and frequency of ECP schedules. Moreover there was variability in cGVHD assessment and endpoints. Despite these pitfalls, the authors concluded that the analysis supported the use of ECP in cGVHD especially in patients with cutaneous, oral and hepatic involvement.

Apisarnthanarax et al. retrospectively analyzed their database of 32 Allogeneic HCT patients with steroid dependent (SD) and steroid resistant (SR) cutaneous cGVHD who were treated with ECP. Patients received a median of 36 ECP sessions over a median of 5.3 months. The complete response rate was 22% and partial response rate was 34%. 64% of patients who were steroid dependent were able to achieve a 50% reduction in steroid dosage while on ECP therapy. On long term follow up, 11 patients (34%) have died due to progression of cGVHD symptoms or infectious complications. Durable CR's were seen in 5 of 7 patients. Patients who presented with progressive cGVHD fared worse than those presenting with de novo cGVHD.

In a recent meta-analysis by abu-Dalle et al. the response rate of ECP after failure of corticosteroid therapy in chronic GVHD was reported as 64%, but responses varied by site of involvement with cGVHD; poor responses were noted in lung (15%). In this meta-analysis significant inter-trial differences were noted in organ-specific response rates and responses based on severity of GVHD were not reported.

In a prospective trial by Foss et al., 25 patients with extensive steroid-refractory chronic GVHD with cutaneous and visceral involvement were assigned to once or twice weekly ECP therapy. The median duration of ECP therapy was 9 months. 20 patients with cutaneous cGVHD and 6 patients with oral cGVHD benefitted from therapy. Steroid sparing and reduction of systemic immunosuppressive therapy was possible in 80% of patients studied. Patients presenting with progressive cGVHD (with history of prior aGVHD) fared much worse than patients who presented with de novo cGVHD. Once or twice weekly ECP had similar outcomes. Overall response rate was reported as 71% for cutaneous cGVHD and 61% in visceral cGVHD. 13 patients developed serious adverse effects from ECP therapy including pneumonia (n=7), CMV colitis (n=1), GI bleed (n=1), urosepsis (n=1), line infection (n=1), catheter associated thrombus (n=1) and disease relapse (n=1).

There are few randomized controlled trials for use of ECP in cGVHD and most physicians use clinical experience and patient response to formulate institutional guidelines regarding frequency and duration of ECP usage. Based on in-house physician expertise in the COH Department of Transfusion Medicine, who have performed thousands of ECP procedures, we utilize an ECP schedule of: 2 procedures per week for the first month, followed by 2 procedures every 2 weeks for the next 3 months. For the purpose of this trial, we will continue using this regimen based on extensive local experience.

In conclusion, ECP is an important tool for use of therapy in steroid refractory and steroid dependent cGVHD with overall response rates of approximately 30% and partial responses in a majority of patients

treated. Responses depend on site of involvement with better outcomes in skin, hepatic, oral and ocular involvement. Patients presenting with de novo cGVHD, without history of preceding aGVHD also tend to respond better. Treatment responses improve with duration of therapy and most patients can gradually be tapered off ECP in 4-6 months. Treatment outcomes are better if instituted early in the course of cGVHD. However, enthusiasm for ECP in patients with cGVHD has to be tempered by the fact that large randomized controlled trials are lacking and few prospective trials have been done in this hard to treat patient population. Moreover, few patients achieve complete remissions, although a majority derives clinical benefit after ECP therapy from disease stabilization and partials responses. In most trials, ECP also helps patients to reduce the amount of steroid use. We believe that the complete and partial response rates should be improved upon by combining this therapy with other agents such as low dose IL-2.

### 2.1.3 Interleukin-2 (IL-2)

Interleukin-2 (IL-2) is a cytokine crucial to regulatory T cell (T-reg) proliferation, activation and survival. It has been safely administered in patients without GVHD undergoing allo-HCT with T-cell depletion. IL-2 can augment the numbers of T-reg and NK cells without inducing GVHD.

T-reg cells (CD4+, CD25+, FOXP3+) account for approximately 5 to 10% of circulating CD4+ T cells. T-reg can modulate immune responses by suppressing auto- and allo-reactive lymphocytes, thus controlling innate and adaptive arms of the immune response. Loss of T-reg function is associated with autoimmune diseases and cGVHD. Cell-mediated immunomodulation may be beneficial in patients with chronic GVHD. In preclinical models, adoptive transfer of T-reg cells has been shown to ameliorate GVHD, but the clinical application of this approach has been challenging. In patients with active cGVHD, low-dose IL-2 can enhance T-reg without increasing the relapse rate of the underlying malignancy and hence may have a role in tipping the balance of the immune system to a more tolerant state. Calcineurin inhibitors, which are standard therapy for most allo-HCT for prevention and treatment of chronic GVHD may impair T-reg expansion and delay immune reconstitution.

Koreth and colleagues conducted a phase I trial of low-dose IL-2 for patients with steroid-refractory chronic GVHD. A total of 29 patients were enrolled. The highest dose level induced unacceptable constitutional symptoms. The maximum tolerated dose of interleukin-2 was  $1 \times 10^6$  IU per square meter. Of the 23 patients who could be evaluated for response, 12 had major responses involving multiple sites. None had progression of chronic GVHD or relapse of a hematologic cancer. The numbers of CD4+ T-reg cells were preferentially increased in all patients, with a peak median value, at 4 weeks, that was more than eight times the baseline value ( $P < 0.001$ ), without affecting CD4+ conventional T cells (T-con). The T-reg:T-con ratio increased to a median of more than five times the baseline value ( $P < 0.001$ ). The T-reg cell count and T-reg:T-con ratio remained elevated at 8 weeks ( $P < 0.001$  for both comparisons with baseline values), then declined when the patients were no longer receiving interleukin-2. The increased numbers of T-reg cells expressed the transcription factor forkhead box P3 (FOXP3) and were able to inhibit autologous T-con cells. Immunologic and clinical responses were sustained in patients who received IL-2 for an extended period, permitting the glucocorticoid dose to be tapered by a mean of 60% (range, 25- 100). Additionally we have in house experience with use of single agent IL-2 (n=7) in patients who have been treated with ECP in the past. In these patients with steroid refractory cGVHD, all patients have derived clinical benefit, either partial response or stable disease, with no serious Grade III/IV adverse events noted at the dose level of 1 million Units /m^2

### 2.1.4 Rationale for combination of ECP and IL2 for cGVHD

As demonstrated in the literature reviewed above, cGVHD is a multisystem disorder caused by impaired immune reconstitution post Allo-HCT with allorecative T cells from donor causing immune mediated organ damage in skin, liver and GI tract. This condition is characterized by relative paucity of T reg

compared to Tcons leading to decline in Treg:Tcon ratio. Normalization of Treg:Tcon ratio is associated with objective clinical improvement in signs and symptoms of cGVHD. ECP has been used successfully in patients with chronic steroid-refractory GVHD, with complete responses noted in 30% of patients. Improvement in cGVHD symptoms in responding patients has been co-related with a concurrent increment in Tregs. Hence ECP is a proven treatment modality in patients with steroid refractory cGVHD and responding patients demonstrate a normalization of Treg:Tcon ratio.

More recently, IL-2 has shown promising results in a phase I dose escalation trial, wherein it was shown to be safe at a dose level of  $1 \times 10^6$  units/m^2 when used in patients with steroid refractory cGVHD. Clinical benefit (partial response and stable disease) 52% of patients on low dose IL-2 therapy. In this trial no complete responses were noted. Co-relative studies demonstrated that patients with cGVHD responding clinically had a significant expansion of T reg pool while on therapy, with responses noted as early as 2 weeks into therapy. This expansion of T regs persisted during the remaining duration of therapy and declined to baseline levels 4 weeks after discontinuation of subcutaneous IL-2. Relapse of cGVHD is noted after discontinuation of IL-2 therapy and this may be related to gradual decline in T regs after stopping IL-2 therapy.

In this phase II prospective trial in patients with steroid-refractory cGVHD, we propose to combine low dose IL-2 with ECP, based on the following:

- A. We hypothesize that combination therapy with IL-2 and ECP will lead to a greater increase in Tregs compared to historic controls when either modality was alone. This is because both ECP and IL-2 boost regulatory T cells (Tregs). The effect of combining ECP and IL-2 on the Treg: Tcon ratio has not been studied in humans and correlative studies will be performed on all patients enrolled on this protocol to evaluate effect of combination therapy on normalizing immune reconstitution post-HCT in patients with steroid refractory cGVHD.
- B. ECP and IL-2 have non-overlapping toxicities; hence, combination of the two should be well tolerated in patients with cGVHD. This combination is already being used off protocol (n=7) at COH after case review and approval by the GVHD committee in patients with cGVHD and the combination is well tolerated in patients treated so far. Patients on this combination have not experienced disease progression and all have derived clinic benefit from disease stabilization or partial responses.
- C. Relapse of cGVHD is frequently noted after discontinuation of IL-2 therapy, possibly related to decline in Tregs to baseline after stopping low dose IL-2 therapy. After completion of protocol specified therapy at 12 weeks, responding patients will continue daily low dose subcutaneous IL-2 (commercial supply) and ECP (per SOP) till clinical benefit is no longer maintained. The decision to continue commercial supply of IL-2 will be per discretion of the treating primary physician in consultation with specialists in cGVHD clinic. No protocol specific monitoring or follow up data will be collected. Monitoring of these patients will be according to acceptable standard of care for patients on cytokine therapy. Ongoing responses will be monitored by the NIH consensus criteria guidelines, again off protocol. We hypothesize that maintenance therapy with IL-2 and ECP will maintain elevated T reg: Tcon ratio, thereby translating into fewer clinical relapses and improved clinical outcomes.

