#### **Clinical Observations and Tests to be Performed:**

Patients will be evaluated for response to intervention (ECP + IL-2) at baseline and at weeks 3, 7, 9, 12 and 16. NIH clinical scoring forms will be used to document responses. Markers of immune activation will be monitored at the same time points from blood samples taken on scheduled clinic visits. Quality of Life Assessments will also be performed at baseline and in weeks 7 and 12.

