#### 5.2 Treatment Schedule

##### 5.2.1 IL-2 Therapy

D. IL-2 will be self-administered by patients as a daily subcutaneous injection. Teaching will be provided before the first subcutaneous injection. The pharmacist, or the primary pharmacy technician working under the supervision of the pharmacist, will prepare the drug under aseptic conditions. The amount (in IU) of drug to be administered will be determined based on body surface area (BSA). The dose should be calculated based on body weight at screening, at a dose of  $1 \times 10^6$  IU/m^2/day for 12 weeks. All treatments will be outpatient based. If however, patients live within a 15 mile distance of the medical center and /or insurance mandates that the IL-2 be given in physician office- IL-2 injections will be given in the infusion center. After completion of 12 weeks of protocol therapy, responding patients will have the option of continuation of therapy till clinical benefit is no longer maintained. IL-2 will be provided by Prometheus Labs for this study. No protocol specific monitoring or follow up data will be collected after initial 12 week period. Monitoring of these patients will be according to acceptable standards of care for patients on cytokine therapy with IL-2. Ongoing responses will be monitored by the NIH consensus criteria guidelines , again off protocol . We hypothesize that maintenance therapy with IL-2 and ECP will

maintain elevated T reg: Tcon ratio, thereby translating into fewer clinical relapses and improved clinical outcomes.

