### **5.3 Planned Duration of Therapy:**

IL-2 and ECP combination therapy will be given for 12 weeks, with final immune assessment occurring at 16 weeks post-initiation of therapy. Patients deemed to be benefiting from combination therapy (i.e. in complete remission, partial remission, minor response or stable disease), will have the options to continue onto the extended duration per discretion of treating physician.

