### **5.4 Optional Extended-duration therapy:**

As mentioned in the section above, patients who are responding to upfront therapy with IL-2 and ECP will be eligible to continue combination therapy with daily subQ IL-2 and ECP per SOP guidelines till clinical benefit is no longer maintained or toxicities develop. While on the optional maintenance therapy, these patients will be monitored for response and toxicity profile in the GVHD clinic on a monthly basis. This monitoring will not require data collection from research staff for response or adverse effect monitoring. Best clinical judgment will be used to determine on each monthly visit on rationale to continue commercial supply IL-2 or not based on clinical benefit and adverse effect profile of IL-2.

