**Chronic GVHD Symptom Score:**

Patients will self-report symptoms and signs of cGVHD using the validated chronic GVHD Symptom Scale. Self-Reported symptom Scales will be obtained at baseline and weeks 3, 7, 9, 12 and 16.

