### 13.1 Study Design, Sample Size, and Accrual Rate

This single center/single arm, phase II clinical trial is designed to evaluate the anti-cGVHD activity of extracorporeal photopheresis (ECP) when combined with low dose IL-2, in patients with steroid refractory cGVHD, as assessed by overall cGVHD response rate (CR+PR+SD). The primary endpoint overall response (CR+PR+SD) is based on the NIH cGVHD consensus criteria; calculated as the percent of evaluable patients that have confirmed CR/PR or SD

This study will implement a Simon, optimal, two-stage design to evaluate the anti-cGVHD activity of the ECP/IL-2 regimen. The trial is expected to enroll 24 patients e sample size is based on the desire to discriminate a promising response rate of 50% from a current response rate of 25%. The null hypothesis

that the true response rate is 25% will be tested against a one-sided alternative. In the first stage, 9 patients will be accrued. If there are 2 or fewer responses in these 9 patients, the study will be stopped. Otherwise, 15 additional patients will be accrued for a total of 24. The null hypothesis will be rejected if 10 or more responses are observed in 24 patients. This design yields a type I error rate of 0.05 and power of .80 when the true response rate is 50%. Currently, about 20-25 new patients are referred to ECP per year. We expect that 6 patients to be enrolled per year with the expected completion of accrual in 4 years.

**Evaluable for Response:** As part of the primary analysis, patients will be considered evaluable for response if they are eligible, have baseline disease assessments, and receive protocol treatment of any duration. All such patients will be evaluated for clinical response. Our primary outcome will be the clinical response rate measured in all patients who are enrolled and receive any amount of protocol therapy.

Patients who are consented for the study but withdraw for any reason (progression of GVHD, infectious complications, insurance denial etc) prior to initiation of protocol therapy will not be eligible for response evaluation.

**Evaluable for Toxicity:** Patients will be considered evaluable for toxicity if they receive any study drug.

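### Sections 2.1.4, 5.2.1 and 5.4 switch off data collection after week 12 for patients who continue IL-2 plus ECP, yet week-16 assessments are scheduled with no exemption for them

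*Combined protocol and SAP*

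**What the plan says.** Three sections remove research data collection once a patient continues past week 12.

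- Section 2.1.4, item C: "After completion of protocol specified therapy at 12 weeks, responding patients will continue daily low dose subcutaneous IL-2 (commercial supply) and ECP". It then says of this phase: "No protocol specific monitoring or follow up data will be collected". Ongoing responses are to be followed off protocol.
- Section 5.2.1 repeats the rule with an explicit cut-off: "No protocol specific monitoring or follow up data will be collected after initial 12 week period".
- Section 5.4, on the monthly clinic visits during extended therapy: "This monitoring will not require data collection from research staff for response or adverse effect monitoring".

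Section 5.3 defines who may continue, at the treating physician's discretion: patients "in complete remission, partial remission, minor response or stable disease".

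Other sections schedule a week-16 assessment and make no exception for these patients.

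- NIH response: the synopsis ("Patients will be evaluated for response to intervention (ECP + IL-2) at baseline and at weeks 3, 7, 9, 12 and 16"), Section 5.2.3 and the study calendar in Section 10.0.
- Symptom Scale, Section 11.2: "Self-Reported symptom Scales will be obtained at baseline and weeks 3, 7, 9, 12 and 16".
- Steroid dose and immune testing, Section 11.2: week 16, or four weeks after the end of treatment.
- Research blood, Section 5.8, and the final immune assessment, Section 5.3: week 16.

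**The concern.** Both instructions cannot be followed for a patient who continues, and the plan does not rank them. The conflict matters because continuation depends on outcome. The groups allowed to continue nearly match the CR+PR+SD definition of response in Section 13.1; minor response is the only addition. If site staff follow the no-data text, whether a week-16 record exists depends on how the patient was doing at week 12. Week-16 summaries of response, symptoms, steroid dose and T-cell subsets would then come from a group depleted of responders.

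Steroid dose is especially exposed. Section 5.2.4 allows a taper only after the first six weeks and only in responders, so late steroid data are most informative in the patients who would be lost. Reducing steroid dosage is a secondary objective in Section 1.2.

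**Working it through.** **1. The plan's own figure.** Section 13.1 stops if there are 2 or fewer responses in 9 patients, and rejects the null at 10 or more in 24, with rates of 25% and 50%. The exact rejection probability is the sum over x = 3 to 9 of P(X1 = x) × P(X2 ≥ 10 − x), with X1 ~ Bin(9, p) and X2 ~ Bin(15, p).

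- p = 0.25: 0.0485 (stated 0.05).
- p = 0.50: 0.8055 (stated 0.80).

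The design reproduces, and no week-16 quantity enters it.

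**2. Do the sections really conflict?** Section 5.2.1 puts the cut-off at week 12, and week 16 lies after it. Section 5.3 names the week-16 immune assessment and the option to continue in consecutive sentences without connecting them.

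**3. Size of the loss if the no-data text is followed.** Let p be the response rate and c the share of responders who continue. The documents give no value for c, so it is an assumption.

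- Records lost = 24 × p × c.
- Records left = 24 − 24pc.
- Responders' share of records left = 24p(1 − c) / (24 − 24pc).

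| p | c | Lost | Left | Responders among records left |
|---|---|---|---|---|
| 25% | 100% | 6 | 18 | 0% |
| 25% | 75% | 4.5 | 19.5 | 1.5/19.5 = 8% |
| 25% | 50% | 3 | 21 | 3/21 = 14% |
| 50% | 100% | 12 | 12 | 0% |
| 50% | 75% | 9 | 15 | 3/15 = 20% |
| 50% | 50% | 6 | 18 | 6/18 = 33% |

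In every row the responders' share of the remaining records is below the true p.

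**4. Effect on a week-16 benefit rate.** As an illustration, assume 50% benefit at week 12, 60% of those continue, 85% of benefit is sustained to week 16, and nobody without benefit at week 12 gains it later.

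- True rate: 0.85 × 12/24 = 42.5%.
- Records left: 24 − 0.6 × 12 = 16.8, of which 4.8 come from patients with benefit at week 12.
- Observed rate: 0.85 × 4.8/16.8 = 24.3%, about 18 points too low.

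With 70% or 90% benefiting at week 12, the same steps give 41% against 60%, and 67% against 77%.

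**5. Other data the same text would remove.**

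- Section 1.2 asks for overall and failure-free survival, non-relapse mortality and relapse through one year, and Section 12.1.3 lists follow-up and survival forms. All of this runs well past week 12.
- Section 7 records adverse events until 30 days after the last IL-2 injection. Even if that means the last protocol dose, 84 + 30 = 114 days, or about 16.3 weeks. If it means the last dose of any supply, the window is longer.

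**6. What week 16 measures.** Section 9.1 defines the last immune sample as four weeks after therapy stops, which is week 12 + 4 for those who complete treatment. A continuing patient is still on therapy at week 16. Section 2.1.4 reports that the regulatory T-cell expansion had returned to baseline four weeks after IL-2 was stopped, so on-therapy and off-therapy samples are not interchangeable.

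**The case against.** The strongest reply is that the no-data sentences are meant only for the extension phase and that the calendar governs the week-16 visit. Section 5.3 gives this some support, and if sites work from the calendar, nothing is lost. That stands as a limit: the defect is an unresolved conflict, and the loss is conditional. It does not remove the conflict, because Section 5.2.1 draws the line at week 12.

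Three stronger readings are tempting, and the documents do not support them.

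- A reader might infer that the primary endpoint is damaged, because Section 13.1 defines it as "calculated as the percent of evaluable patients that have confirmed CR/PR or SD" and week 16 is the only scheduled assessment after week 12. But no section defines confirmation as a repeat visit, and Section 11.1 reads as confirmation by the NIH criteria. The endpoint is response to a 12-week course, and stable disease already counts. The primary immunologic endpoint in Section 9.1 is at three months.
- A reader might infer that the observed week-16 benefit rate would fall close to zero. That needs every benefiting patient to continue, and continuation is optional. Patients who leave for toxicity, lost insurance cover or withdrawal (Section 5.5) may also be in partial response or stable disease.
- A reader might infer from the absence of progression in the earlier IL-2 trial and the clinical benefit in all seven in-house patients (Section 2.1.4 and the IL-2 background before it) that nearly all patients would benefit and be lost. Section 2.1.4 also gives clinical benefit of 52% in that trial, and the design target is 50%.

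It is also fair to say that Section 13.2 names no week-16 estimate, so the harm is to secondary and correlative results.

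**Conclusion.** The contradiction is real and the sections must be reconciled. If the no-data text is followed, week-16 secondary and correlative data are lost selectively in benefiting patients who continue. At a 50% response rate that is 12, 9 or 6 of 24 for continuation shares of 100%, 75% or 50%. These counts assume that the trial reaches its second stage, and the shares are assumptions; the direction of the selection is the same for all of them. The same text also conflicts with the one-year outcome objectives and with the adverse event recording window. The 12-week response endpoint and the Simon design are not shown to be affected.

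**What to change.** In Sections 2.1.4, 5.2.1 and 5.4, limit the no-data statement to extension-phase monitoring beyond the protocol's scheduled assessments. A sentence barring all data after week 16 would not do, because it would contradict the one-year objectives and the adverse event window. Then state that:

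- the week-16 NIH response, Symptom Scale, steroid-dose and immune assessments are done in every treated patient, including those who continue;
- one-year outcome status (Section 1.2) and adverse event recording (Section 7) still apply to them, with the last IL-2 injection defined for patients who continue;
- continuation status is recorded, and week-16 immune results are reported separately for patients on and off therapy, in view of the definition in Section 9.1.

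The cost is a few sentences, CRF entry for one visit, and the already planned week-16 research blood and assays in continuing patients. One-year status follow-up is already required by the objectives, and continuing patients attend the GVHD clinic monthly under Section 5.4.
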